#### **4.2.2 Main Analytical Approach for Primary Estimand**

The primary estimand is the difference in time to onset of cCDP12, as expressed by the HR, between the higher and approved dose of ocrelizumab arms in patients with RMS and regardless of adherence to the randomized treatment or use of an approved MS disease-modifying therapy (DMT) medication. More specifically, the estimand has the following attributes:

**Population:** Patients with RMS.

**Endpoint:** Time to onset of cCDP12.

**Summary Measure and Primary Estimator:** The HR will be used to quantify the difference in time to onset of cCDP12 between study treatments, and will be estimated from a Cox proportional hazards regression model, stratified by the randomization stratification factors. The statistical significance of the estimated HR will be calculated by using the log-rank test, stratified by the randomization stratification factors.

In order to estimate the primary estimand, the following **intercurrent event** handling strategies will be applied:

**Early discontinuation from study treatment:** All data pre and post treatment discontinuation will be included in the analysis following the treatment-policy strategy.

**Initiation of an approved MS DMT medication:** All data pre and post initiation of alternative MS treatment will be included in the analysis following the treatment-policy strategy.

**Pregnancy:** All data pre and post pregnancy onset will be included in the analysis following the treatment-policy strategy.

**Death:** This is anticipated to be very rare, but in case of occurrence, it will be handled as a progression event in line with the composite strategy.

Every effort will be made to collect the data post early discontinuation from study treatment or initiation of an approved MS DMT medication until primary analysis.

Intermediate missing assessments at scheduled visits prior to the last EDSS, 9-HPT, or T25FWT assessments will not be imputed. For patients with initial disability progression based on EDSS or  $\geq 20\%$  increase in T25FWT or 9-HPT, data collected at the next scheduled visit or treatment discontinuation visit will be used to confirm disability progression.

Missing data resulting from patients that withdraw their consent to participate in the study and/or a serious GCP breach will not be imputed.

Patients without any prior progression events during the DBT phase will be censored at their last EDSS, 9-HPT, or T25FWT assessments (administrative censoring).

### **4.2.3 Sensitivity Analysis**

The following sensitivity analyses of the primary estimand will be conducted according to the analysis described in Section 4.2.2.

1. The primary analysis is performed under the assumption that patients who have initial progression at their last EDSS, T25FWT or 9-HPT assessment prior to withdrawal from study are similar to those who remain in the study in terms of their risk of cCDP12. This is because such patients are censored at their last EDSS, T25FWT or 9-HPT assessment. To assess the potential violations of this assumption, the robustness of the estimated treatment effect to violations of this assumption will be investigated by repeating the primary analysis with the following imputation rules:

For patients who had initial progression at the time of premature withdrawal from the study, multiple imputation will be used to either impute a progression event or to censor the time to onset of confirmed progression at their last EDSS, T25FWT or 9-HPT assessment prior to withdrawal from the study. The presence or absence of a progression event at the last EDSS, 9-HPT, or T25FWT assessment prior to withdrawal from the study will be imputed from a Bernoulli distribution with success probability ranging from 0-1 in increments of 0.33. This procedure will be applied within arms followed by treatment effect estimation in 100 imputed data sets. An overall estimate of the treatment effect and associated standard error for computing 95% Wald intervals will be obtained by applying Rubin's rules on the log HR scale and then back transforming to the original scale:

$$\log(HR) = 1/100 \sum_{m=1}^{100} \log(HR_m) \text{ and } SE(\log(HR)) = \sqrt{V_W + \left(1 + \frac{1}{100}\right) V_B},$$

where  $HR_m$  is the HR estimated in the  $m$ th imputed data set,  $V_W$  is the sample mean of the estimated variance of  $\log(HR_m)$ , and  $V_B$  is the sample variance of  $\log(HR_m)$ .

The scenarios that result in non-significant treatment effect estimates will be identified for a tipping point analysis.

2. The primary analysis is performed under the independent censoring assumption. However, this assumption may not be plausible if treatment discontinuation affects the chance of prematurely withdrawing from study as well as cCDP12. If at least 10% participants have withdrawn from the study without having the cCDP12 event, it will be attempted to predict onset of cCDP12 event times for patients who prematurely withdraw from study based on observed post treatment discontinuation data. This prediction is deemed to be feasible only if a sufficient number of patients (i.e., at least 5% of patients) have at least one EDSS/T25FWT/9HPT assessment after treatment discontinuation. This approach of imputing missing data is aligned with the treatment policy approach for handling premature discontinuation of study treatment, since it accounts for the fact that patients who have withdrawn from study will no longer be on study treatment.

The proposed sensitivity analysis is based on the multiple imputation approach in [Hartley et al. 2022](#), which build on the sensitivity analysis strategy in [Jackson et al. 2014](#). Specifically, the following steps will be applied:

- a) Fit a time-varying Weibull model with hazard function  $\exp(\alpha)time^{\exp(\alpha)-1} \exp\{\beta_0 + \beta_1 X_i + \beta_2 T_i + (\gamma_0 + \gamma_1 T_i)1(time > D_i)\}$  to time to onset of cCDP12. Here,  $\alpha, \beta_0, \beta_1, \beta_2, \gamma_0, \gamma_1$  are unconstrained parameters to be estimated,  $time$  is time from randomization,  $X_i$  is a vector containing the baseline EDSS, T25FWT and 9-HPT values for patient  $i$ ,  $T_i$  is an indicator such that  $T_i=1$  if patient  $i$  was randomized to the higher dose of ocrelizumab arm and  $T_i=0$  otherwise, and  $D_i$  is the time from randomization to discontinuation from study treatment.
- b) Simulate 100 sets of  $\{\alpha, \beta_0, \beta_1, \beta_2, \gamma_0, \gamma_1\}$ , from the estimated asymptotic normal distribution of the maximum likelihood estimator of these parameters.
- c) Let  $W_i$  and  $F_i$  be the times from randomization for patient  $i$  at the time of withdrawal from the study and end of the study. For each set of simulated parameter values, generate onset of cCDP12 event times for patients who have not had cCDP12 up to and including  $W_i$ , and where  $W_i < F_i$ . This will result in 100 complete analysis data sets, i.e., where cCDP12 events times are either available or are censored at  $F_i$ . In order to simulate cCDP12 events time  $O_i$  for patient  $i$ , the following formula will be used:

$$O_i = \{W_i^{\exp(a)} - \log(U_i)\exp(-\beta_0 - \gamma_0 - \beta_1 X_i - \beta_2 T_i - \gamma_1 T_i)\}^{1/\exp(a)}$$

Here,  $U$  is generated from a standard uniform distribution. If  $O_i > F_i$ , the onset time of cCDP12 is recorded as censored at  $F_i$  in the analysis data set, otherwise it is set to  $O_i$ .

- d) For each of the 100 complete analysis data sets, estimate the log HR and its associated standard error with the Cox model used for the primary analysis. Then, use Rubin's rules to combine the estimates from the 100 complete data sets, as described in sensitivity analysis 1, to obtain an overall estimate of the treatment effect on the HR scale and associated 95% Wald interval.

It is worth noting that the proposed sensitivity analysis slightly differs from that in [Hartley et al. 2022](#). In particular, the proposed analysis follows one of the suggestions of [Jackson et al. 2014](#), which is to use a parametric imputation model and account for the uncertainty in the estimation of the parameters indexing the imputation model by simulating from the estimated maximum likelihood estimator of these parameters. In contrast, the approach in [Hartley et al. 2022](#) requires fitting a semi-parametric imputation model to multiple bootstrap samples in order to account for the uncertainty in the estimation of the baseline hazard and other parameters indexing the imputation model. Compared to the approach in [Hartley et al. 2022](#), the proposed approach should therefore be less susceptible to convergence issues when there are a few observed cCDP12 events after treatment discontinuation, since the imputation model only needs to be fitted to the observed data instead of multiple bootstrap samples.

In the absence of sufficient data to perform the multiple imputation described above (i.e., at least 5% of patients should have at least one EDSS/T25FWT/9HPT assessment after treatment discontinuation), the robustness of the independent censoring assumption will be evaluated using a tipping point analysis.

Multiple imputation will be used to either impute a progression event or to censor the time to onset of confirmed progression at their last EDSS, T25FWT or 9 - HPT assessment prior to withdrawal from the study. The presence or absence of a progression event at the last EDSS, 9-HPT, or T25FWT assessment prior to withdrawal from the study will be imputed from a Bernoulli distribution with success probability ranging from 0-1 in increments of 0.33. This procedure will be applied within arms followed by treatment effect estimation in 100 imputed data sets. An overall estimate of the treatment effect and associated standard error will be estimated as described in sensitivity analysis 1. The scenarios that result in non-significant treatment effect estimates will be identified for a tipping point analysis.

3. The primary analysis will be conducted using actual study days to estimate cCDP12 event times and treatment effects. Due to the periodic nature of assessments, the exact timing of cCDP12 events is unknown, as events are recorded at the next scheduled assessment after the event, resulting in interval-censored data. To assess the potential impact of using actual event days on estimation and hypothesis testing, a sensitivity analysis using interval censoring methods will be performed.

For each patient, the left and the right boundaries of the interval will be derived based on the following rules:

Situations	Left Boundary	Right Boundary
Patients who had cCDP12	The date of the last assessment that showed a disease progression-free* status	The date of the first assessment that showed cCDP12
Patients who did not have cCDP12	The date of the last assessment that showed a disease progression-free* status	Not applicable (Missing)
Patients who died and did not have cCDP12 prior to death	The date of the last assessment that showed a disease progression-free* status	Death date

cCDP12= 12-week composite confirmed disability progression

\* For patients who did not have any post-baseline assessment with disease progression-free status, the left boundary is the date of randomization.

The survival curves will be estimated using the non-parametric maximum likelihood estimate (NPMLE, [Turnbull 1976](#)) for each treatment arm.

Hypothesis testing will be performed based on the stratified log-rank test proposed by Sun ([Sun 1996](#)) to compare the cCDP12 in the treatment arms. The treatment effect will be estimated using a stratified proportional hazard regression model ([Finkelstein 1986](#)) with a parametric assumption of piecewise exponential distribution for the baseline hazard function ([Friedman 1982, Royston and Parmar 2002](#)).

The analyses listed above will be performed using the procedures PROC ICLIEFTTEST and PROC ICPHREG in Statistical Analysis System (SAS) version 9.4 or a later version.

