6.4 EFFICACY ANALYSES

The analysis population for the efficacy analyses will consist of all randomized patients, with patients grouped according to their assigned treatment.

For analysis purposes, treatment discontinuation will be defined as 24 weeks after the last dose.

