## **4. STATISTICAL ANALYSES**

### **4.1 GENERAL CONSIDERATIONS**

All statistical hypotheses for the primary and secondary endpoints and treatment comparisons will be tested at the 5% significance level ( $\alpha=0.05$ ) against two-sided alternatives.

All primary and secondary efficacy endpoints will be stratified by region, age at screening, baseline EDSS and baseline body weight for analysis. The regional stratifications are United States and ROW. The age categories are  $\leq 45$  years and  $> 45$  years. The EDSS categories are  $< 4.0$  and  $\geq 4.0$ . The body weight categories are  $< 75$  kg and  $\geq 75$  kg.

The baseline for the primary endpoint is the date of randomization. The baseline value of the endpoint, e.g., EDSS, T25FWT and 9-HPT values, is the most recent value up to and including the date of randomization but before first infusion of study drug. A subject with delayed dosing may receive the first dose 2 weeks after the baseline visit; if an EDSS, T25FW or 9-HPT score is recorded between the randomization date and the date of the first dose, this value will be considered as a post-baseline assessment.

FAS will be used in the analysis of the primary and secondary estimands, and exploratory efficacy endpoints. Safety analysis set (SAS) will be used to summarize safety data. For analysis purposes, the time of treatment discontinuation will be defined as 24 weeks after the last dose prior to the date of treatment discontinuation recorded in the electronic Case Report Form (eCRF).

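### Sensitivity analysis 2 imputes from the off-treatment hazard at withdrawal, but the fitted model starts that hazard only at last dose plus 24 weeks, so the draw is inconsistent for patients who leave sooner

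*SAP*

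**What the plan says.** Three parts of the SAP bear on this point.

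- **The fitted model (4.2.3, sensitivity analysis 2, step a).** A Weibull hazard for time to cCDP12 includes the extra term gamma0 + gamma1*T_i only while time exceeds D_i, which "is the time from randomization to discontinuation from study treatment".
- **The date of discontinuation (4.1).** The SAP's convention for its analyses is that "the time of treatment discontinuation will be defined as 24 weeks after the last dose prior to the date of treatment discontinuation recorded"; the recorded date is the eCRF one. Protocol 6.4 has the same rule: "treatment discontinuation will be defined as 24 weeks after the last dose".
- **The imputation (4.2.3, sensitivity analysis 2, step c).** The plan will "generate onset of cCDP12 event times for patients who have not had cCDP12 up to and including" the withdrawal time W_i, provided W_i is earlier than the end-of-study time F_i. The formula starts from W_i and always includes gamma0 and gamma1*T_i. D_i does not appear in it, and there is no condition that W_i be at or after D_i.

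The reason given for the approach is that "it accounts for the fact that patients who have withdrawn from study will no longer be on study treatment".

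The analysis is conditional. It is attempted only if at least 10% of participants withdraw without a cCDP12 event and at least 5% of patients have an EDSS, T25FWT or 9-HPT assessment after discontinuing treatment. If those post-discontinuation data are insufficient, a tipping point analysis replaces it.

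**The concern.** The fit and the imputation use different switch times for the same hazard change. Infusions are 24 weeks apart, so a patient on schedule who leaves before the next one is due has W_i earlier than last dose plus 24 weeks, which is D_i. The schedule of activities in Protocol Appendix 1 foresees withdrawal either together with stopping drug or later, so both W_i < D_i and W_i >= D_i can occur.

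Take two patients with the same last dose. The first stops drug but stays in the double-blind phase, and contributes on-treatment hazard to the fit until D_i. The second leaves the study, and is imputed at the off-treatment hazard at once. The gammas are estimated only from time after D_i but applied to time before it.

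What is at stake is the fidelity of the analysis meant to probe the independent censoring assumption behind the primary result. It should draw from the model that it fitted, and the text should not leave two programmers free to treat D_i differently.

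**Working it through.** **1. The plan's own figure.** SAP 2.2 gives 205 events for 80% power at HR 0.66, with 2:1 allocation and two-sided 5%. The Schoenfeld formula gives (1.960 + 0.842)^2 / [(2/3)(1/3)(ln 0.66)^2] = 7.85 / (0.2222 x 0.1727) = 205 events, and 205 events give 80.1% power. This reproduces and does not depend on step (c).

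**2. The algebra.** Write k = exp(alpha), eta_on = beta0 + beta1*X + beta2*T, eta_off = eta_on + gamma0 + gamma1*T and E = -log(U). With a constant linear predictor eta, the step (a) hazard integrates to t^k exp(eta). A patient event-free at W has an event time O that solves H(O) - H(W) = E.

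- If W >= D, eta_off applies throughout and O = {W^k + E exp(-eta_off)}^(1/k). This is exactly the SAP formula.
- If W < D, eta_on applies from W to D and eta_off after D, so the solution has two pieces. The SAP formula uses eta_off over the whole interval, starting D - W too early. With 24-week dosing, that gap is between 0 and 24 weeks for a patient on schedule.

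**3. One patient.** Assumed: control arm, k = 1, 21.5% progression per 2 years (the SAP gives 21.5% without a time basis), W = 1.5 years, F = 3.5 years, off-treatment hazard doubled, gap 24 weeks = 24/52.18 = 0.460 year. The on-treatment hazard is -ln(0.785)/2 = 0.1210 per year.

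- Imputed risk inside the gap: SAP 1 - exp(-2 x 0.1210 x 0.460) = 10.5%; fitted model 1 - exp(-0.1210 x 0.460) = 5.4%.
- Imputed risk by F: SAP 1 - exp(-2 x 0.1210 x 2) = 38.4%; fitted model 1 - exp(-[0.1210 x 0.460 + 0.2421 x 1.540]) = 34.9%.
- If the off-treatment hazard were instead 0.8 times the on-treatment hazard, the figures by F would be 17.6% (SAP) and 18.5% (fitted model), so the sign reverses.
- With no off-treatment effect the two draws are identical.

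**4. Trial level.** From SAP 2.2: 865 patients, 2:1 allocation, 5% annual dropout, HR 0.66. Assumed: k = 1, 21.5% per 2 years, follow-up 2.3 to 4.1 years, dosing on schedule, and every withdrawer with W < D. This gives about 113 event-free withdrawers and a mean gap of about 12 weeks. Both draws in a row use the same random numbers and an unstratified Cox model. Rows are separate runs, so hazard ratios should be compared only within a row. An exp(gamma1) of 1.52 = 1/0.66 means that the higher-dose benefit is lost off drug.

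| exp(gamma0) | exp(gamma1) | Imputed events, SAP / two-piece | HR, SAP / two-piece |
|---|---|---|---|
| 1.0 | 1.00 | 16.9 / 16.9 | 0.6577 / 0.6577 |
| 1.5 | 1.00 | 23.8 / 22.8 | 0.6617 / 0.6618 |
| 2.0 | 1.00 | 30.3 / 28.5 | 0.6558 / 0.6554 |
| 1.0 | 1.52 | 20.8 / 20.3 | 0.6822 / 0.6791 |
| 1.5 | 1.52 | 29.6 / 28.0 | 0.6979 / 0.6944 |
| 2.0 | 1.52 | 38.0 / 35.4 | 0.6997 / 0.6944 |
| 3.0 | 1.52 | 49.6 / 45.7 | 0.7044 / 0.6996 |

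Where the gammas are not both zero, the excess is 0.5 to 3.9 imputed events. The hazard ratio differs by at most 0.0053. With half the withdrawers at W >= D, the 2.0 / 1.52 case gives 37.4 against 36.0 events and HR 0.7003 against 0.6975, about half the effect.

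**The case against.** The strongest reply is that step (c) states an assumption and contains no slip. The SAP says that withdrawn patients are no longer on study treatment, and step (c) treats them so from W_i. SAP 4.5.1.2 ends treatment duration at the earliest of several dates, including study withdrawal. If D_i were read as the earlier of last dose plus 24 weeks and W_i, the formula would be exact and the fit unchanged, because no follow-up after W_i enters the fit.

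That reading is coherent, but the SAP does not state it. The rule in 4.5.1.2 is for exposure only, and it lists the Section 4.1 discontinuation date and study withdrawal as separate dates. SAP 4.7 is silent. Followed as written, the plan draws from a hazard inconsistent with the fitted one, so even this reading needs a sentence and a justification.

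Other parts of the reply stand. The parameters and the Weibull form are the same in both steps; only the switch time differs. Patients who stop drug are meant to stay in the double-blind phase, and those who leave at or after last dose plus 24 weeks are imputed correctly. The size depends on assumed gaps. With 86 withdrawers, a base hazard of 0.10 per year and an off-treatment hazard 1.5 to 3 times as high, the excess is 0.8 to 2.4 imputed events if gaps are uniform over 0 to 24 weeks. It is 0.4 to 1.2 if exits fall equally at the visits 12 and 24 weeks after a dose.

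**Conclusion.** The mismatch is real and minor. Step (c) is the exact draw from the fitted model only when W_i >= D_i. For W_i < D_i it starts the off-treatment hazard up to 24 weeks early. In the scenarios tried, with every withdrawer affected, this changes imputed events by about 1 to 4 and the hazard ratio by about 0 to 0.005. These sizes rest on assumed gammas, Weibull shape, follow-up and time basis for the control rate, none of which the documents give.

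Three stronger readings are tempting and are not supported:

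- A reader might infer that most withdrawers are affected. The documents give no count with W_i < D_i.
- A reader might infer that the analysis over-imputes events, or distorts the arms differently. Over-imputation requires a higher off-treatment hazard, and how far the arms differ depends on gamma1; both are unknown. If the benefit is lost off drug, the hazard ratio is pulled slightly toward 1, against the superiority claim, but that direction is not guaranteed.
- A reader might infer that the primary result is in doubt. The primary test, the 205 events and the power do not use step (c). One conditional sensitivity analysis is affected.

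**What to change.** Make step (c) two-piece. With k, E, eta_on and eta_off as defined in the working, for W_i < D_i:

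- if E <= (D_i^k - W_i^k) exp(eta_on), set O_i = {W_i^k + E exp(-eta_on)}^(1/k);
- otherwise set O_i = {D_i^k + [E - (D_i^k - W_i^k) exp(eta_on)] exp(-eta_off)}^(1/k).

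Keep the present formula for W_i >= D_i, and censor at F_i as now.

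If the sponsor does intend the off-treatment hazard to apply from withdrawal, the SAP should instead state that D_i = min(last dose + 24 weeks, W_i) for this analysis. It should also justify why a patient who leaves is off treatment sooner than one who stops drug and stays.

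The cost is a small code change and a short SAP amendment. The amendment is a real step, since this SAP version was signed on 18 February 2025, after the cutoff that SAP 2.3 scheduled for December 2024. Reporting the number of imputed withdrawers with W_i < D_i would show how far the choice matters.

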#### **4.2.4 Supplementary Analyses**

The following supplementary analyses of the primary endpoint will be conducted according to the analysis described in Section [4.2.2](#):

1. The primary analysis will be repeated after excluding patients who meet the following exclusion criteria/do not meet the following inclusion criteria at baseline:
  - History of primary progressive MS at screening
  - Known presence of other neurological disorders that may mimic MS
  - Any concomitant disease that may require chronic treatment with systemic corticosteroids or immunosuppressants during the course of the study
  - History of or currently active primary or secondary (non-drug-related) immunodeficiency
  - Pregnant or breastfeeding

- Previous use of anti-CD20s (including ocrelizumab), unless the last infusion was more than 2 years before screening, B-cell count is normal, and the stop of the treatment was not motivated by safety reasons or lack of efficacy
- Treatment with any investigational agent within 24 weeks prior to screening (Visit 1) or five half-lives of the investigational drug (whichever is longer), or treatment with any experimental procedure for MS (e.g., treatment for chronic cerebrospinal venous insufficiency)
- Any previous treatment with mitoxantrone, cladribine, atacept, alemtuzumab, and daclizumab
- Previous treatment with fingolimod, siponimod, or ozanimod within 6 weeks of baseline
- Previous treatment with natalizumab within 4.5 months of baseline
- Previous treatment with interferons beta (1a or 1b), or glatiramer acetate within 2 weeks of baseline
- Previous treatment with any other immunomodulatory or immunosuppressive medication not already listed above without appropriate washout as described in the applicable local label (washout to be completed prior to baseline). If the washout requirements are not described in the applicable local label, then the wash out period must be five times the half-life of the medication. The pharmacodynamic (PD) effects of the previous medication must also be considered when determining the required time for washout
- Any previous treatment with bone marrow transplantation and hematopoietic stem cell transplantation
- Any previous history of transplantation or anti-rejection therapy
- Treatment with IV Ig or plasmapheresis within 12 weeks prior to randomization
- No Diagnosis of RMS (i.e., relapsing-remitting multiple sclerosis or active secondary progressive multiple sclerosis where patients still experience relapses) in accordance with the revised McDonald Criteria 2017
- Less than two documented clinical relapses within the last 2 years prior to screening, or no clinical relapse in the year prior to screening (with no relapse 30 days prior to screening and at baseline)
- Not neurologically stable within 30 days prior to randomization and baseline assessments
- EDSS scores at screening and baseline greater than 5.5
- Average T25FWT score over two trials at screening and over two trials at baseline respectively, above 150 seconds
- Average 9-HPT score over four trials at screening and over four trials at baseline respectively, above 250 seconds

- No documented MRI of brain with abnormalities consistent with MS at screening
- Randomized to the higher dose arm and with an incorrect classification of body weight into the strata  $<75$  kg or  $\geq 75$  kg

In addition, the hypothetical strategy will be used to handle the following intercurrent events:

- Early discontinuation from study treatment
- Initiation of approved MS DMT medication
- Two consecutive missed assessments of EDSS, T25FWT and 9-HPT
- Erroneously received a quantity of ocrelizumab (including no ocrelizumab) other than the group to which the patient was randomized
- Received study drug that had been mishandled (e.g., incorrect storage temperature) and was not approved for subsequent use
- Received ocrelizumab / ocrelizumab placebo but was not randomized

Under this strategy, the data after these intercurrent events will be treated as missing and the time to onset of cCDP12 will be censored at the last assessments prior to the intercurrent event times. However, the observed data after the intercurrent events will still contribute to the confirmation period for determining if an initial progression can be confirmed. This analysis estimates the treatment effect of the higher dose of ocrelizumab in a population who always receives the study treatment as planned and without consecutive missing assessments of the primary endpoint.

2. The primary analysis will be repeated after removing the individual components from cCDP12 one at a time. This analysis will determine the extent to which the treatment effect is driven solely by each of the individual components.
3. The primary analysis will be repeated after increasing the threshold for disability progression based on the performance tests from  $\geq 20\%$  to  $\geq 25\%$  and  $\geq 30\%$ . This analysis will assess the sensitiveness of the treatment effect to the influence of the performance tests on cCDP.
4. The primary analysis will be repeated after expanding the definition of the individual component endpoints in cCDP to include the following requirements between the initial progression and confirmation visit:
  - $< 20\%$  decrease in T25FWT and/or 9-HPT from baseline and
  - $< 1.0$  decrease in EDSS from baseline if baseline EDSS  $\leq 5.5$  or  $< 0.5$  decrease in EDSS if baseline EDSS  $> 5.5$

This analysis will assess the sensitiveness of the treatment effect to the presence of cCDP12 events where disability improvement occurs in one or

more of the component endpoints during the confirmation period. This analysis will also be repeated for cCDP24.

5. The primary analysis will be applied to the time to onset of cCDP12 or study drug discontinuation due to AE. Thus, this supplementary analysis will incorporate discontinuation of the study drug due to AE into the definition of treatment benefit.
6. The primary analysis will be repeated (i) after censoring all patients from Russia and/or Ukraine at the onset of the Russia-Ukraine war (24th Feb 2022) and (ii) in patients not from Russia and/or Ukraine. These analyses will assess the impact of the Russia-Ukraine war on the primary analysis.

